8.2.2 Vital Signs

The following vital signs will be assessed in accordance with the Schedule of Procedures (Appendix 1):

- Blood pressure (systolic and diastolic; mmHg).
- Resting heart rate (beats per minute).
- Body temperature (°C or °F; oral, core [rectal], axillary or tympanic).
- Weight.
- Height (screening only).

Vital signs will be measured after resting in a seated position for 5 minutes.

8.2.3 Physical Examinations

Physical examinations will be performed in accordance with the Schedule of Procedures (Appendix 1).

A full physical exam will be performed at screening. Detailed/brief (system-guided) physical examinations will be done at subsequent time points to evaluate any clinically significant abnormalities, including worsening of conditions included in the patient's medical history.

8.2.4 Electrocardiograms

Single standard 12-lead digital ECGs will be performed in accordance with the Schedule of Procedures (Appendix 1).

The ECG (measured after resting in a supine position for 5 minutes) will include heart rate, rhythm and RR, PR, QRS, and QTc intervals. The ECG will be read and interpreted at the investigational site for patient safety monitoring and documentation will be stored with the source documents.

8.2.5 Left Ventricular Ejection Fraction (LVEF)

Multiple-gated acquisition scan or ECHO scans to determine LVEF will be performed in accordance with the Schedule of Procedures ([Appendix 1](#)).

Screening ECHO/MUGA scans must be performed within 28 days prior to randomization.

It is strongly recommended to use the same method of cardiac evaluation (ECHO or MUGA) at each relevant time point for each patient.

8.3 Other Assessments

8.3.1 Pharmacokinetics

At selected study centers, PK samples will be collected from approximately 100 patients in the neratinib plus capecitabine arm (Arm A) on Days 1 and 15 of Cycle 1, as noted in the Schedule of Procedures (Appendix 1). Patients should be instructed to report the exact time that the dose of neratinib was taken on the days of PK sample collection.

8.3.2 Health Outcomes Assessments

The following health outcomes assessments will be completed by patients, as noted in the Schedule of Procedures (Appendix 1):

- European Organisation for Research and Treatment of Cancer Quality of Life Questionnaire-C30 (EORTC QLQ-C30), version 3 ([Appendix 8](#))
- EORTC QLQ-BR23 (breast cancer-specific questionnaire; [Appendix 9](#))
- EuroQol (EQ-5D-5L) multi-dimensional health status questionnaire ([Appendix 10](#))

8.3.3 ECOG Performance Status

Eastern Cooperative Oncology Group performance status will be assessed in accordance with the Schedule of Procedures (Appendix 1). The ECOG categories are summarized in [Appendix 3](#).

Screening ECOG performance status may be accepted as the baseline status if the assessment was performed within 72 hours before randomization and there are no clinically significant findings.

8.4 Protocol Deviations

Protocol deviations should be reported to the Sponsor (or designee).

8.5 Patient Diary

The Patient Diary used for recording of investigational product intake during the first 2 cycles. The number of stools per day will also be recorded on the Patient Diary for the first 2 cycles. In addition, patients in the neratinib treatment arm will record the use of loperamide/other antidiarrheal treatment taken along with the dose of neratinib for the first 2 cycles.

9 STUDY CONDUCT

A Schedule of Procedures is provided in Appendix 1.

In addition to the procedures listed below, unscheduled clinic visits and procedures should be performed at the Investigator's discretion to assess symptoms and concerns newly reported by the patient to rule out or confirm potential recurrence, or for the purpose of assessing the patient's safety.

9.1 Screening/Baseline

Screening activities are to be conducted within 21 days prior to randomization. Baseline assessments must be done within 72 hours before randomization. Randomization should occur after all baseline assessments have been completed and the site confirms that the patient still meets all eligibility requirements.

The following information and assessments will be performed, collected and/or recorded at screening in accordance with the Schedule of Procedures (Appendix 1):

- Signed ICF for the study.
- Collect demography: date of birth, sex, race (Asian, Black or African American, White, Native Hawaiian or Pacific Islander, American Indian or Alaskan Native, Other), and ethnicity (Hispanic or Latino, Non-Hispanic or Non-Latino).
- Medical history:
 - Record chronic conditions and/or medical history of significance (including the review of history of cardiac, pulmonary and gastrointestinal disease), relevant surgical procedures and symptoms experienced during the previous 30 days as well as those ongoing at the time of screening, and any medical conditions that require medication.
 - Cancer history, including but not limited to: date of first diagnosis, nodal status (based on pathologic assessment of nodes at the time of surgery, either before adjuvant chemotherapy or after completion of neoadjuvant chemotherapy), histology, tumor stage at diagnosis, predictive and prognostic biomarkers, previous chemotherapy/biotherapy/ immunotherapy, previous adjuvant therapy (drug names, start and stop dates, reason for TD), previous radiation, and prior cancer-related surgical therapies.
 - Other previous and concomitant medication will be documented, as described in Section 7.
- Physical examination. Refer to Section 8.2.3.

- Vital signs, height and weight. Refer to Section 8.2.2.
- ECG. Refer to Section 8.2.4.
- LVEF (ECHO or MUGA). Refer to Section 8.2.5.
- ECOG performance status. Refer to Section 8.3.3.
- Serum pregnancy test. Refer to Section 8.2.1.
- Laboratory tests (urine dipstick, hematology and serum chemistry panel). Refer to Section 8.2.1.
- Radiographic (or other appropriate modality for) tumor assessment (RECIST v1.1). Refer to Section 8.1.2.
- In addition, following signing of informed consent, tumor tissue must be prepared and sent for central laboratory confirmation of HER2 expression and hormone receptor status (Refer to Section 8.2.1.1).

The following assessments will be performed at baseline in accordance with the Schedule of Procedures (Appendix 1):

- Physical examination. Refer to Section 8.2.3.
- Vital signs, height and weight. Refer to Section 8.2.2.
- ECOG performance status. Refer to Section 8.3.3.
- Health outcomes assessments. Refer to Section 8.3.2.
- Laboratory tests (urine dipstick, hematology and serum chemistry panel). Refer to Section 8.2.1.

9.2 Active Treatment Phase

Neratinib (Arm A) or lapatinib (Arm B) will be self-administered by patients once daily during each 21-day cycle. Capecitabine will be self-administered by patients BID on Days 1 to 14 of each 21-day cycle (Arm A and B).

The following will be performed during the active treatment phase in accordance with the Schedule of Procedures (Appendix 1):

- Physical examination. Refer to Section 8.2.3.
- Vital signs and weight. Refer to Section 8.2.2.

- ECG. Refer to Section 8.2.4.
- LVEF. Refer to Section 8.2.5.
- ECOG performance status. Refer to Section 8.3.3.
- Health outcomes assessments. Refer to Section 8.3.2.
- Concomitant medication assessment. Refer to Section 7.
- Adverse event assessment. Refer to Section 13.
- Laboratory tests (hematology and serum chemistry panel). Refer to Section 8.2.1.
- Radiographic (or other appropriate modality for) tumor assessment. Refer to Section 8.1.2.
- Dispense investigational product. Refer to Sections 6.1.
- Review the Patient Instructions for the management of diarrhea with the patient and dispense antidiarrheal medication. Refer to Section 7.1.1.
- Review entries in the Patient Diary through Cycle 2. Refer to Section 8.5.
- Treatment compliance assessment. Refer to Section 6.3.
- PK sampling. Refer to Section 8.3.1.

9.3 Treatment Discontinuation Visit

The TD visit will be used to perform safety assessments and should be completed within 3 days after the last dose of investigational product.

The following will be performed in accordance with the Schedule of Procedures (Appendix 1):

- Physical examination. Refer to Section 8.2.3.
- Vital signs and weight. Refer to Section 8.2.2.
- ECG. Refer to Section 8.2.4.
- LVEF. Refer to Section 8.2.5.
- ECOG performance status. Refer to Section 8.3.3.
- Health outcomes assessments. Refer to Section 8.3.2.
- Concomitant medication assessment. Refer to Section 7.
- Adverse event assessment. Refer to Section 13.
- Laboratory tests (hematology and serum chemistry panel). Refer to Section 8.2.1.

- Treatment compliance assessment. Refer to Section 6.3.

Patients who remain on study will enter the long-term follow-up phase after the TD visit. Adverse events will continue to be monitored until the 28th day after the last dose of investigational product.

If a patient discontinues from the study for a reason other than disease progression or withdrawal of consent, he/she will continue CT/MRI assessments every 6 weeks, starting from Cycle 1/Day 1.

9.4 Safety Follow-up Contact

Patients will be contacted by phone 28 days (+5 days) after the last dose of investigational product to collect AE, cancer therapy (anti-cancer medication, cancer-related radiotherapy, and cancer-related surgery), concomitant medication, and survival information.

9.5 Long-term Follow-up Phase

Patients who discontinue study therapy will be followed for survival status during the long-term follow-up phase. If a patient discontinued study therapy due to toxicity, tumor assessments will continue to be performed at 6-week intervals throughout the long-term follow-up phase, until documented disease progression, death, or withdrawal of consent. Patients will also be contacted every 12 weeks for survival status and to collect the following data:

- Anti-cancer medications, including dose and regimen, taken since last contact.
- Cancer-related radiotherapy administered since last contact.
- Cancer-related surgeries/procedures performed since last contact.

The long-term follow-up phase will continue until patient death or withdrawal of consent. Survival follow-up will occur via telephone call if the site is unable to confirm status via chart review.

If a patient withdraws from the long-term follow-up phase of the study, attempts should be made to contact the patient to determine the reason(s) for discontinuation (see Section 10.3).

Patients who are no longer continuing with scheduled study visits will be followed for SAEs until the patient starts a subsequent cancer therapy (see Section 13.3).

9.6 End of Study

The EOS will occur as of the date of the last visit of the last patient undergoing the study. In the event that the EOS is declared earlier, investigational product(s) will be available to patients who continue to receive clinical benefit as described in Section [4.1](#).

10 PATIENT WITHDRAWAL AND REPLACEMENT

10.1 Investigational Product Discontinuation

Withdrawal due to an AE should be distinguished from withdrawal due to other causes and recorded on the appropriate AE CRF page.

If one of the two investigational products given in combination has been discontinued, patients may continue to receive the other investigational product as monotherapy, at the Investigator's discretion. This is applicable to both treatment arms of the study. Reintroduction of the discontinued investigational product at a later time during the active treatment phase is not permitted.

Patients **must** be discontinued from **investigational product(s)** (but may remain in the study, if appropriate) under the circumstances listed below and in [Appendix 2](#), unless otherwise agreed with the Medical Monitor.

- If the patient requires more than two dose reductions of the investigational product(s) (see [Appendix 2](#)).
- If investigational product(s) is withheld due to an AE for >28 days.
- Disease progression.
- Initiation of alternative anti-cancer therapy. Any concurrent chemotherapy, radiotherapy (including palliative radiotherapy), surgery related to cancer, anticancer immunotherapy, or other anticancer treatments including other investigational agents, megestrol and hormonal agents are prohibited (see Section [7.3](#)).
- Pregnancy (see Section [13.4](#)).
- Investigator request.
- Patient request (i.e., withdrawal of consent for treatment).

10.2 Withdrawal from the Study

Patients may withdraw from the **entire study, including follow-up**, at any time without penalty and for any reason without prejudice to his or her future medical care. Study withdrawal may occur for the following reasons:

- At the discretion of the Investigator.
- At the patient's request (withdrawal of consent for the study).

- Lost to follow-up (defined as three failed attempts to contact by phone, followed by one attempt by sending a certified letter).
- If the entire study is terminated prematurely as described in Section 11.

A patient may also be withdrawn from **investigational product/study** by the Sponsor, Regulatory Authorities, or Independent Ethics Committees (IEC)/IRBs.

10.3 Procedures for Patient Withdrawal

When a patient is withdrawn from the study, the Investigator will notify the Sponsor. In all cases, the reason(s) for premature discontinuation/withdrawal and the primary reason must be recorded on the CRF. If a patient is prematurely withdrawn from the investigational product or the study for any reason, the Investigator must make every effort to perform the evaluations described for the TD visit, the safety follow-up contact 28 days later, and a follow-up visit 12 weeks later. If a patient discontinues due to an AE, he/she should continue to be under medical supervision until symptoms cease or the condition becomes stable.

If a patient withdraws consent but agrees to undergo a final examination, this will be documented on the CRF and the Investigator's copy of the ICF, which will be countersigned and dated by the patient.

If a patient is lost to follow-up or voluntarily withdraws from study participation, every effort should be made to determine why the patient was lost to follow-up or withdrew consent. This information, including the date, should also be recorded on the patient's conclusion of patient participation CRF.

All patients will remain on active study treatment until treatment or study discontinuation, death, or withdrawal of consent. Upon confirmed disease progression, or discontinuation of randomly assigned investigational product for any other reason, all further anti-cancer treatment will be at the Investigator's discretion. All patients will remain in the long-term follow-up phase for survival unless consent has been withdrawn or until death.

10.4 Patient Replacement

Patients will not be replaced.

11 PREMATURE TERMINATION OF THE STUDY

The Sponsor may suspend or terminate the study or part of the study at any time for any reason. Investigational product(s) will be available to patients who continue to receive clinical benefit following the EOS as described in Section 4.1.

If the Investigator suspends or terminates the study, the Investigator will promptly inform the Sponsor and the IRB/IEC and provide them with a detailed written explanation. The Investigator will also return all investigational products, investigational product containers and other study materials to the Sponsor or have them destroyed locally according to Sponsor guidelines. Upon study completion, the Investigator will provide the Sponsor, IRB/IEC and regulatory agency with final reports and summaries as required by regulations. For investigational new drug application studies, the Investigator must submit a written report to the Sponsor and the IRB/IEC within 3 months after the completion or termination of the study.

12 STATISTICAL METHODS

The statistical considerations summarized in this section outline the plan for data analysis of this study. Additional details of the analysis will be provided in a Statistical Analysis Plan (SAP), which will be finalized prior to unblinding the data. Any deviations from the protocol or SAP-specified analyses will be identified in the clinical study report.

A final PFS analysis will be conducted when 419 PFS events have occurred and a final OS analysis will be conducted when 378 deaths have occurred. An interim analysis of OS will be conducted at the time of the final PFS analysis.

12.1 General Considerations

The primary efficacy analysis will be performed on the intent to treat (ITT) population, defined as all patients randomized into the study. Formal definitions of the analyses populations are provided in the SAP.

12.2 Study Patients

12.2.1 Disposition of Patients

The number and percentage of patients entering and completing each phase of the study will be presented, stratified by treatment. Reasons for withdrawal pre- and post-randomization will also be summarized.

12.2.2 Demographics, Medical History, Baseline Characteristics, and Concomitant Medications

Demographic data, medical history, baseline characteristics including predictive and prognostic biomarkers, concomitant disease, and concomitant medication will be summarized by means of descriptive statistics (n, mean, standard deviation, median, minimum and maximum) or frequency tables, overall and stratified by treatment.

12.2.3 Treatment Compliance

Duration of treatment will be summarized separately for each investigational product by treatment group. In addition, the cumulative quantity, dose intensity (quantity per time unit) and the relative dose intensity (dose intensity/scheduled dose per time unit) will be summarized. The number of patients with dose holds or dose reductions will be tabulated for each investigational product by treatment group.

12.3 Efficacy Analyses

12.3.1 Primary Efficacy Analysis

The co-primary endpoints are independently adjudicated PFS and OS. PFS is defined as disease progression demonstrated by radiographic imaging or other appropriate modality, or death due to any cause. Tumor evaluations will be performed by a central review vendor.

Patients will be stratified at randomization by whether they had 2 or ≥ 3 prior HER2+ MBC regimens in the metastatic setting, their geographic region (North America vs. Europe including Israel vs. Rest of World), disease category (visceral vs. non-visceral only), and hormone receptor status (ER and/or PR positive vs. ER and PR negative). All efficacy endpoints will be summarized by treatment group and visit when appropriate.

The efficacy assessment in PFS will be assessed by a blinded, independent, central review of tumor assessments for all patients at screening, and then after every 6 weeks from first dose of investigational product, regardless of treatment schedule modification (e.g., dose delay), until documented disease progression or death. PFS will be independently-assessed using RECIST v1.1.

Missed tumor assessments must be performed as soon as possible. Patients who discontinue from study treatment for a reason other than radiographically confirmed (or confirmation by other appropriate modality) objective disease progression will have radiological tumor assessments performed approximately every 6 weeks from the date of the last tumor assessment until documented disease progression or death.

Survival data will be collected throughout the active treatment phase and during the long term follow-up phase. Survival follow-up after patient discontinuation of investigational product will be conducted approximately every 12 weeks to assess for survival until patient's death, withdrawal of consent, or the EOS.

12.3.1.1 *Statistical Methods*

When 419 PFS events have occurred the primary PFS analysis will be performed. The median time to PFS and corresponding two-sided 95% confidence intervals will be calculated using the product limit estimator and displayed using a Kaplan-Meier graph, by treatment group. A log-rank test controlling for hormone receptor status, number of prior HER2-directed regimens in the metastatic setting, visceral disease, and geographic region strata will be used to test the null hypothesis of no difference in the time to PFS between the two treatment groups at the alpha level of 0.01. Subjects who discontinue therapy early will be censored at their last available time point. Sensitivity analyses will be performed to investigate the impact of differential dropout between the two treatment groups on the treatment effect estimate.

When the PFS analysis is performed, an interim analysis will be performed on the OS endpoint. When 378 deaths have occurred, primary OS analysis (final analysis) will be performed. The median time to PFS and corresponding two-sided 95% confidence intervals will be calculated using the product limit estimator and displayed using a Kaplan-Meier graph, by treatment group. A log-rank test controlling for hormone receptor status, number of prior HER2-directed regimens in the metastatic setting, visceral disease status, and geographic region strata will be used to test the null hypothesis of no difference in the hazard between the two treatment groups at the alpha level of 0.002 at the interim analysis and 0.038 for the final analysis.

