8.1.2.1 General Information

All target and non-target sites of disease (see [Appendix 7](#)) identified at screening must be followed for the duration of the study. Their presence and absence should be noted throughout follow-up. Overall response for each patient is based on the combined results of target and non-target lesions and the presence or absence of new lesions.

Tumor-based efficacy endpoints (i.e., PFS and ORR) will be based on tumor assessments, which are performed by the Investigators. Response and progression will be evaluated using RECIST v1.1 ([Appendix 7](#)).

Tumor assessments will be performed for all patients at 6-week intervals throughout the active treatment phase, starting from Cycle 1/Day 1 until documented disease progression, death, or withdrawal of consent, regardless of whether the patient is continuing or has discontinued study treatment. Additional tumor evaluations will be performed as clinically indicated. Missed tumor assessments must be performed as soon as possible. As soon as evaluations for each tumor assessment are completed, the Investigator should assess the patient's overall response (target plus non-target lesions) based on criteria and overall response algorithms as defined in RECIST v1.1 ([Appendix 7](#)). Scans (and/or good color photographs with a ruler for skin lesions) must be assessable for all evaluations.

The longest diameters (LD) for all non-nodal target lesions and the short axis diameter (SAD) of nodal target lesions will be recorded. The LD for all non-nodal target lesions and the SAD of nodal target lesions will be added and reported as the baseline sum longest diameter (SLD). Per RECIST v1.1, for determining CR or PR, all post-baseline tumor measurements will be compared with the baseline SLD; for determining PD, the post-baseline measurement is compared with the smallest SLD recorded since initiation of treatment, including baseline (see [Appendix 7](#)).

Patients who discontinue study treatment for reasons other than PD per RECIST will continue to be followed up by protocol for scheduled tumor assessments until PD, and long-term for OS (see [Section 10.3](#)).

For patients who show a CR on one scan and on a confirmatory scan obtained 6 weeks later, the frequency of subsequent scans may be reduced at the discretion of the investigator to no less than one scan every 12 weeks.

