12.7 Determination of Sample Size

The co-primary endpoints will be analyzed using an overall Type I error rate of 0.01 for PFS and 0.04 for OS. To detect a hazard ratio (control versus treatment) of 0.70 with approximately 85% power, 419 PFS events (PD/deaths) are required to be observed; this assumes a median (ITT) PFS of 8.0 months (34.7 weeks) for the experimental arm (neratinib plus capecitabine) and 5.6 months (24.3 weeks) for the control arm (lapatinib plus capecitabine). It is expected that the 419th event will be observed at approximately 26 months after the first patient is enrolled, which would correspond to approximately half of the death events needed to be observed. At this time, an interim analysis on OS will also be performed. For the OS endpoint, a group sequential method will be employed to maintain the overall Type I error rate at 0.04. Specifically, O'Brien-Fleming boundaries will be calculated to create appropriate critical values to which the log rank statistic will be compared.

Information Fraction	Expected Death Events	Study Month	Boundary (Reject H ₀)	Significance Level
50%	185	26	3.066	0.002
100%	378	50	2.058	0.038

These boundaries are designed to detect a hazard ratio (control versus treatment) of 0.725 with approximately 85% power. Overall, 378 events (deaths) are required to be observed; this assumes a median (ITT) OS of 30.3 months for the experimental arm (neratinib plus capecitabine) and 22.0 months for the control arm (lapatinib plus capecitabine). Approximately 600 patients will be enrolled and randomized equally between the two treatment arms.

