2.6. Sample Size Determination

The co-primary endpoints will be analyzed using an overall Type I error rate of 0.01 for PFS and 0.04 for OS. To detect a hazard ratio (experimental vs. control) of 0.70 with approximately 85% power, 419 PFS events (PD/Deaths) are required to be observed; this assumes a median (ITT) PFS of 8.0 months (34.7 weeks) for the experimental arm (neratinib plus capecitabine) and 5.6 months (24.3 weeks) for the control arm (lapatinib plus capecitabine).

It is expected that the 419th event will be observed at approximately 26 months after the first subject is enrolled, which would correspond to approximately half of the death events needed to be observed. At this time, an interim analysis on OS will also be performed. For the OS endpoint, a group sequential method will be employed to maintain the overall Type I error rate at 0.04. Specifically, Lan DeMets alpha spending function approximating the O’Brian-Fleming boundaries will be calculated to create appropriate critical values to which the log rank statistic will be compared (De Mets and Gordon Lan, 1994). If 50% of the deaths are observed at the interim OS analysis, the boundary using the Lan-DeMets alpha spending function is shown in Table 1 for OS interim analysis.

Table 1: Spending Function

Information Fraction	Expected Death Events	Study Month	Boundary (Reject H_0)	2-Sided Significance Level*
50%	185	26	3.066	0.002
100%	378	50	2.058	0.039

* This significance level relates to the 0.04 alpha allocation to OS but will be updated if the entire 0.05 can be allocated to OS.

These boundaries are designed to detect a hazard ratio (experimental vs. control) of 0.725 with approximately 85% power. Overall, 378 OS events (deaths) are required to be observed; this assumes a median (intent to treat [ITT]) OS of 30.3 months for the experimental arm (neratinib plus capecitabine) and 22.0 months for the control arm (lapatinib plus capecitabine).

Approximately 600 subjects will be enrolled and randomized equally between the two treatment arms. This sample size assumes a 1% drop out rate per 12 months (52 weeks) equally distributed between the treatment arms for the PFS endpoint.

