8.2.1. Progression Free Survival (PFS)

Progression free survival (PFS) is defined as the time interval from the date of randomization until the first date on which recurrence, progression (per RECIST v1.1), or death due to any cause, is documented. It is not necessary to confirm disease progression.

All tumor assessments and deaths collected will be used except in the following 2 cases:

1. If a subject misses 2 or more consecutive assessments immediately prior to the documentation of PD or death the subject will be censored at the last assessment prior to the missed visits (following the FDA guidance on clinical trial endpoints for the approval of cancer drugs and biologics).
2. For subjects that started a new anti-cancer therapy, all tumor assessments and deaths after the start date of new anti-cancer therapy will be excluded from the analysis.

After taking into account the two conditions listed above, subjects without documented PD or death, including those who dropped out, will be censored at their last tumor assessment. Patients who did not have any tumor assessments after the screening visit will be censored on the randomization date.

Assessment of PFS will be performed by a blinded, independent, central review of tumor assessments for all patients at Screening, and then after every 6 weeks from first dose of investigational product, regardless of treatment schedule modification (e.g., dose delay), until documented disease progression or death. PFS will be assessed using the Response Evaluation Criteria in Solid Tumors (RECIST v1.1).

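### The protocol's primary PFS text censors patients who stop therapy early without limiting this to patients who have no progression or death, which conflicts with its own PFS definition and with SAP 8.2.1

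*Protocol*

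**What the plan says.** Protocol 12.3.1.1 describes the primary PFS analysis at 419 events and then states: "Subjects who discontinue therapy early will be censored at their last available time point". The synopsis has the same sentence under its efficacy analysis. Neither place adds a condition.

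Other parts of the plan bear on the same patients:

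- **Protocol 8.1.1** defines PFS and gives two censoring points: the last assessable evaluation and the start of new anticancer therapy. Stopping study drug is not named.
- **SAP 8.2.1** says "All tumor assessments and deaths collected will be used except in the following 2 cases". The cases are two or more consecutive missed assessments just before the event, and the start of new anti-cancer therapy. Only patients with neither progression nor death are then censored, at their last tumor assessment.
- **Protocol 8.1.2.1** requires 6-weekly tumor assessments "regardless of whether the patient is continuing or has discontinued study treatment". Section 12.3.1 and Appendix 1 (footnotes i and q) also continue scans after discontinuation until progression or death.
- **On precedence**, Protocol 12 says the SAP adds detail, and SAP Section 1 says the SAP supplements the protocol. SAP Section 11, meant for changes from the protocol, holds only a placeholder.

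**The concern.** As worded, early discontinuation is itself the reason for censoring. A censored patient contributes no event, so a progression or death seen on a required off-treatment scan would drop out of a co-primary endpoint. Two censoring rules for that endpoint therefore stand side by side in an open-label trial.

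Such censoring would be potentially informative. Protocol 7.1.1 calls diarrhea the major dose-limiting toxicity of neratinib, so early stops may differ by arm. Protocol Appendix 7 and Section 6.1 of the supplemental SAP recognise patients who stop for deterioration or clinical progression without RECIST progression. The literal rule would censor these patients just when an event is likely.

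The count of PFS events also triggers both the PFS analysis and the OS interim, so the rule affects when those analyses take place.

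**Working it through.** **1. The rules side by side**

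| Patient who stops study drug before progression | Protocol 12.3.1.1, literal | Protocol 8.1.1 | SAP 8.2.1 |
|---|---|---|---|
| Progresses on a later scheduled scan, no new therapy | Censored | Event | Event |
| Starts new therapy, then progresses | Censored | Censored | Censored |
| Progresses or dies after two or more missed assessments | Censored | Not addressed | Censored |
| No progression or death | Censored | Censored at last assessable evaluation | Censored at last tumor assessment |

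The first row is the clear conflict.

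**2. The plan's own figure**

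Inputs from Protocol 12.7: an alpha of 0.01 allotted to PFS; the event target, given as "To detect a hazard ratio (control versus treatment) of 0.70 with approximately 85% power, 419 PFS events (PD/deaths) are required to be observed"; and medians of 8.0 and 5.6 months, where 5.6/8.0 = 0.70. Two-sided testing is assumed for PFS; the SAP labels only its OS boundary table "2-Sided Significance Level".

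Freedman: events = (z₀.₉₉₅ + z₀.₈₅)² × [(1 + HR)/(1 − HR)]² = (2.576 + 1.036)² × (1.70/0.30)² = 13.05 × 32.11 = 419. This is an exact match. The one-sided version gives 364. Schoenfeld gives 411, and 85.9% power at 419 events. The target does not depend on the censoring rule.

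**3. Timing of the 419th event**

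Assume exponential PFS with λ = ln 2/8.0 and ln 2/5.6 per month, 300 patients per arm, uniform accrual over A months and 1% dropout per year (SAP 2.6). For a patient entering at month u, with total censoring hazard μ:

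P(event by month T) = λ/(λ + μ) × [1 − exp(−(λ + μ)(T − u))], averaged over u from 0 to A.

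Under the literal rule, μ also includes a stopping hazard, equal in both arms, set so that an average share p stops before progression. The documents give neither A nor p; both are assumed.

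| p | Events at month 26 (A = 24) | Month of 419th event (A = 24) | Month of 419th event (A = 18) | Maximum events |
|---|---|---|---|---|
| 0 | 417 | 26.1 | 22.1 | 595 |
| 10% | 392 | 27.8 | 23.7 | 536 |
| 20% | 364 | 31.2 | 26.9 | 477 |
| 30% | 333 | never | never | 418 |

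The delay is 1.7 months (27.8 − 26.1) or 1.6 months (23.7 − 22.1) at p = 10%. At p = 20% it is 5.1 months (31.2 − 26.1) or 4.8 months (26.9 − 22.1). At p = 30% the maximum of 418 falls short of 419.

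**4. Effect on the hazard ratio**

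This is a simulation with 400,000 patients per arm, exponential PFS, a control median of 5.6 months and administrative censoring at 24 months. The stopping hazard is λp/(1 − p), and the hazard after stopping is k times λ. The literal rule is modelled as censoring at the stop. The comparator follows every patient to the event.

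| On-treatment HR | Stops, neratinib / control | k | Full follow-up | Literal rule |
|---|---|---|---|---|
| 0.70 | 20% / 10% | 1 | 0.697 | 0.697 |
| 0.70 | 20% / 10% | 2 | 0.727 | 0.700 |
| 0.70 | 20% / 10% | 3 | 0.742 | 0.699 |
| 0.70 | 10% / 20% | 2 | 0.655 | 0.701 |
| 0.70 | 10% / 20% | 3 | 0.640 | 0.700 |
| 0.70 | 10% / 10% | 2 | 0.695 | 0.701 |
| 0.70 | 10% / 10% | 3 | 0.694 | 0.700 |
| 1.00 | 20% / 10% | 2 | 1.057 | 1.000 |
| 1.00 | 20% / 10% | 3 | 1.078 | 0.999 |
| 1.00 | 10% / 20% | 2 | 0.944 | 0.997 |
| 1.00 | 10% / 20% | 3 | 0.926 | 0.999 |

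A separate simulation of the 20% / 10% case with an on-treatment HR of 0.70 (150 replicates per scenario) gave 0.73 to 0.75 with full follow-up, against 0.70 to 0.71.

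**The case against.** The strongest reply is that the sentence is only loosely worded and the SAP already settles the matter. Protocol 10.1 lists disease progression among the reasons for stopping, so the sentence cannot mean that everyone who stops is censored. The next sentence in 12.3.1.1 concerns dropout. The last available time point could therefore be the last scan, on or off treatment, for a patient without an event, which would agree with SAP 8.2.1. The SAP also has a sensitivity analysis using all assessments and deaths (8.3.1.1, item 3). Much of this stands: the milder reading is possible, and the practical risk is limited if the SAP is followed. But the sentence lacks the condition that would make the milder reading the only one, and nothing says the SAP overrides the protocol.

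The objections to the size also stand:

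- The text does not name the stop date as the censoring date, so step 4 models one reading.
- The SAP rule is not full follow-up. It still censors at new anti-cancer therapy and after two missed assessments, so the differences in step 4 are upper limits on what the rewording can change, provided those two rules remove follow-up about equally in both arms. The delays in step 3 are upper limits too.
- The 20% against 10% split is assumed. Protocol 2.2.3.4 reports 6% stopping neratinib plus capecitabine because of diarrhea and few stops for toxicity overall, and Section 7.1.1 makes antidiarrheal prophylaxis mandatory in the neratinib arm.

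A reader might also infer that the planned 26 months shows which rule was intended. It does not, because accrual is unstated. No early stops with 24-month accrual gives month 26.1; 20% stops with 18-month accrual gives month 26.9.

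**Conclusion.** The conflict is in the text and does not depend on any assumption: Protocol 12.3.1.1 and the synopsis, taken as written, disagree with Protocol 8.1.1 and SAP 8.2.1 on whether a progression or death after stopping study drug is a PFS event. The off-treatment scanning rule governs data collection, so it is not itself a competing analysis rule. It shows that the data would be collected and then not used for PFS.

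The consequence is conditional on the literal sentence being applied, on stopping being related to prognosis, and on the assumed stop rates and post-stop hazards. In the unequal-stop scenarios with an on-treatment hazard ratio of 0.70, the hazard ratio shifts by roughly 0.03 to 0.06.

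Three stronger conclusions are tempting but not supported:

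- **Bias in favour of neratinib.** The direction follows the arm with more early stops. With more stops on control, the literal rule understates the neratinib effect.
- **Departure from intention to treat.** Protocol 12.1 and SAP 4.1 define a population, and all randomized patients stay in it. What would be lost is follow-up time and events.
- **Loss of power at the analysis.** The trigger is a count of events, so the main effect is delay unless early stops approach 30%.

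This should be corrected, but it does not undermine the design.

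**What to change.** Replace the sentence in Protocol 12.3.1.1 and in the synopsis with wording such as:

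> Discontinuation of study treatment is not a reason for censoring. Progression and death after discontinuation count as PFS events, subject only to the two rules in SAP 8.2.1. A patient with neither event is censored on the date of the last tumor assessment.

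Record the difference between the protocol text and SAP 8.2.1 in SAP Section 11, which is now an unfilled placeholder.

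The cost is a wording amendment to the protocol and an entry in the SAP. No new data are needed, and the 419-event target, the alpha and the power are unchanged. Some potentially informative censoring will remain through the new-therapy and missed-assessment rules; the all-assessments sensitivity analysis in SAP 8.3.1.1 already addresses it.
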